4.2.5 End of Study

For individual patients, the end of the study will be as follows:

- Should no diagnosis be made 12 months after inclusion into the study, the patient will leave the study and perform the end of study visit
- Patients diagnosed with a non-ILD condition will leave the study on the date of diagnosis

- Patients diagnosed with IPF or non-IPF ILD will remain in the study and be followed up to the start of drug treatment (within six months) or a maximum of six months if no drug treatment is prescribed

4.3 ANALYSIS OF TREATMENT GROUP COMPARABILITY

Not applicable.

4.4 ANALYSIS OF STUDY CONDUCT

4.4.1 Patient Disposition

An overview on patient disposition, showing number and percentages of patients screened (patients who have signed informed consent), screening failures, patients enrolled, patients who completed the study at the end of pre-diagnosis or post-diagnosis period, patients with and without start of treatment and patients that prematurely discontinued the study will be provided by diagnosis cohorts and separately by country and center. Centers are thereby classified into “community sites” and “tertiary sites”. An actual list of sites with the allocation to “community” and “tertiary” can be found on [Appendix 5](#). For patients who discontinued the study prematurely, frequencies of reasons for early discontinuation will be provided. In addition, a listing specifying the patient disposition status and reasons for early discontinuation will be presented.

4.4.2 Major Protocol Deviations

The Investigator should document and explain any protocol deviation. The Investigator should promptly report any deviation that might have an impact on patient safety and data integrity to the Sponsor and to the IRB/EC in accordance with established IRB/EC policies and procedures. The Sponsor will review all protocol deviations and assess whether any represent a serious breach of Good Clinical Practice guidelines and require reporting to health authorities. As per the Sponsor's standard operating procedures, prospective requests to deviate from the protocol, including requests to waive protocol eligibility criteria, are not allowed.

A table summarizing major protocol deviations will be provided by diagnosis cohorts, and protocol deviations will be also listed.

4.4.3 Demographic and Baseline Characteristics

Baseline and disease characteristics such as demographics, female reproductive status, tobacco and alcohol use history, and medical history and baseline conditions assessment will be summarized by descriptive statistics or frequency tables. Tables will be displayed by the different diagnosis cohorts. Moreover, demographic and baseline characteristics listing will be presented.

4.4.3.1 Demographics

The following demographic characteristics will be summarized:

- Age (years): date of birth – date of enrollment visit, and age categories (18-64; 65-84; >=85 years)
- Gender
- Race (in case that more than one race will be ticked, a concatenated variable, containing all races will be presented (e.g. Asian/White))
- Ethnicity
- Weight, height and Body Mass Index (BMI) = $\text{weight}(\text{kg})/\text{height}(\text{m})^2$
- Female reproductive status
- Tobacco use history and nicotine exposure
- Alcohol use history and alcohol consumption, that will be presented only in the final analysis.
- Home spirometry and accelerometry : FVC (mL) and steps per day.

4.4.3.2 Medical History

Medical history and baseline conditions assessments will be coded using the Medical Dictionary for Regulatory Activities (MedDRA®), version 21.1 or above and will be listed and summarized presenting numbers and frequencies by primary System Organ Class (SOC) and Preferred Term (PT) by diagnosis cohorts. If patients have more than one disease within a SOC or PT they will be counted only once for the respective SOC or PT.

4.4.3.3 Subgroups

In addition, an overview table displaying the number of patients of the different subgroups that are used to investigate exploratory objectives will be given. The table includes the following subgroups:

- Patients from community/tertiary sites
- Countries involved in the study
- Patients with/without post-diagnosis period
- Patients with/without at least 3 months of observation time from first day after the time window for calculation of baseline from home spirometry until EOS

- Patients having/not having at least one lung biopsy
- Progressing/non-progressing patients: progressing patients are characterized by a semi-annual decline in FVC of > 50 ml (using home-based spirometry measurements) and/or >15% decline (absolute difference) in steps/day at the end of the study compared to baseline. The average of the last 7 days measurements will be compared with baseline (defined in Section [4.2.2](#)). Patients not fulfilling these requirements are defined as non-progressing patients. Data up to the end of study visit will be used for the assignment of progressing/non-progressing patients in order to compare the semi-annual FVC decline and steps/day during the whole peri-diagnosis period.
- Patients requiring/not requiring at least one respiratory-related hospitalization (as documented by the investigator in the eCRF)
- ILD subgroups: for non-IPF ILD patients ILD subgroups are defined based on types of ILD as ticked by the investigator in the eCRF, i.e.
 - Collagen = ILD of known causes – Collagen
 - HP = HP (hypersensitivity pneumonitis)
 - NSIP = Idiopathic NSIP: Non-specific interstitial pneumonia
 - uILD = uILD (Unclassifiable ILD)
 - Other = all other types of ILD

In addition to the described baseline characteristics there are several patient population characteristics that are assessed during or at the end of the peri-diagnosis period. These assessments will therefore be analyzed as post-baseline characteristics.

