4.2.2 Baseline Observations

After discussion of the results of the first interim analysis from December 2018 with the SC in January 2019 it was decided to re-define the calculation for baseline FVC from home spirometry and steps per day from accelerometry. This new definition is given in Table 2 below.

Table 2 Definition of Baseline Observations

	Definition
Baseline data for site visit measurements	Baseline is defined as the measurement collected at the enrollment visit of each assessment.
Baseline data for home measurements	Baseline is defined as the average of the daily measurements collected during the next 7 consecutive days after the first 7 days removed, counted from the day of the first acceptable manoeuvre flagged as 'Good blow' of home spirometry after enrollment visit as defined in Table 1.

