
 • To further characterize the disease behavior of IPF and non-IPF ILD in the peri-diagnostic period using a multidimensional approach 	
 • Change in pulmonary function (FVC measured in mL and % predicted by site spirometry) • Change in physical functional capacity (measured by daily home accelerometry and site 6-minute walk test [6MWT]) • Change in PRO measures, overall 
 ○ Change in PRO measures during the pre-diagnosis period ○ Changes in PRO measures during the post-diagnosis period • Correlation between home and site spirometry measurements of FVC • Correlation between physical functional capacity assessed at home (by accelerometry) and on site (by 6MWT) • Comparison of disease behavior in IPF and ILD patients • Evaluate the baseline characteristics of progressing vs non-progressing patients, patients requiring respiratory-related hospitalizations • Incidence of non-elective hospitalization, both respiratory and all cause • Incidence of Investigator-reported acute exacerbations ^a • Incidence of death, all cause and respiratory-related deaths • Incidence of events related to the study assessments
Exploratory objectives	

 • Characterization of different subgroups 	
 • Evaluate the characteristics (baseline characteristics, changes in pulmonary function and physical activity) of different ILD subgroups, e.g. connective tissue disease associated ILD, chronic hypersensitivity pneumonitis ILD, etc., depending on available data • Evaluate the characteristics (baseline characteristics, changes in pulmonary function and physical activity) of patients with no diagnosis made 12 months after inclusion into the study

 • Evaluate the differences in FVC values at beginning of treatment, depending on reimbursement restrictions 	
 • Differences in pulmonary function (FVC measured in mL by daily home spirometry and site spirometry) at the start of IPF drug treatment with regards to applicable local reimbursing restrictions for pirfenidone treatment in patients with IPF

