From inclusion into the study, patients will be followed for a maximum of 12 months in the pre-diagnosis assessment period. Following thorough assessments and diagnoses, three groups of patients will be identified:

- Patients diagnosed with IPF.
- Patients diagnosed with an ILD other than IPF.
- Patients diagnosed with a condition that is not an ILD.

For individual patients, the end of the study will be as follows:

- Should no diagnosis be made 12 months after inclusion into the study, the patient will leave the study.
- Patients diagnosed with a non-ILD condition will leave the study on the date of diagnosis.
- Patients diagnosed with IPF or non-IPF ILD will remain and be followed in the study up to the start of drug treatment (within six months) or a maximum of six months if no drug treatment is prescribed.

“Start of drug treatment” is defined as the date when treatment commences. This includes the event of a patient receiving IPF or ILD drug treatment from a physician other than the investigator.

Accordingly, the total length of the study is variable for each patient, with a maximum of 18 months.

Site visits will be conducted at a minimum at baseline, diagnosis, and end-of-study for each individual patient. During each study period (pre- and post-diagnostic period), every patient should have at least one site visit, scheduled at the discretion of the Investigator. During these visits, any relevant information such as treatments given and results from HRCTs, radiographs, DLCO, lung biopsies etc. will be collected, as available.

The 6MWT and FVC measurements will be assessed on-site as per the Schedule of Activities (Appendix 1).

The study will be conducted under the leadership of a Steering Committee.

In the absence of the use of any therapeutic agent, an Independent Review Committee IRC/IRF or a Data Safety Monitoring Board (DSMB)/ Data Monitoring Committee (DMC) will not be needed in this study.

Patient study-specific assessments / study kit

Upon study enrollment, each patient will receive a study kit with a unique identifier containing the following:

- Hand-held spirometer (Device to measure daily FVC at home).
- Accelerometer (Device to continuously measure daily activities, such as steps per day, physical activity level).

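### The progressing/non-progressing label depends partly on time in study: the steps criterion is not time-scaled, the FVC derivation is ambiguous, and short or missing series default to non-progressing

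*SAP*

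**What the plan says.** Section 4.4.3.3 (Subgroups) defines progressing patients by two criteria joined by and/or:

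- FVC: "semi-annual decline in FVC of > 50 ml (using home-based spirometry measurements".
- Steps: ">15% decline (absolute difference) in steps/day at the end of the study compared to baseline".

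It then says "The average of the last 7 days measurements will be compared with baseline", without stating whether this covers both measures or steps only. The default follows: "Patients not fulfilling these requirements are defined as non-progressing patients". The closing sentence says data up to the end-of-study visit are used "in order to compare the semi-annual FVC decline and steps/day during the whole peri-diagnosis period".

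Other parts of the SAP bear on this:

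- Section 4.5.1 derives each patient's time-adjusted semi-annual decline as the regression slope × 183.
- Section 4.2.2 sets the home baseline as the "average of the daily measurements collected during the next 7 consecutive days after the first 7 days removed", so roughly days 8 to 14 of home data.
- Section 4.2.5 ends follow-up at the start of drug treatment for diagnosed IPF and ILD patients, with no minimum. Appendix 1 says "the total length of the study is variable for each patient, with a maximum of 18 months".
- Appendix 1, Table 3 lists under the secondary objectives: "Evaluate the baseline characteristics of progressing vs non-progressing patients".
- Section 4.5.5 repeats the primary endpoint in every Section 4.4.3.3 subgroup. It also repeats the baseline tables by this label, including how long the pre- and post-diagnosis periods lasted.

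**The concern.** A label meant to separate faster from slower decliners should mean the same thing whether a patient was observed for one month or eighteen. A fixed percentage fall measured at a variable end point does not do that: a slow decliner followed for long can cross the bar, while a faster decliner whose series stops early may not. The FVC criterion is worded as a rate, but it is followed by a sentence describing an end-versus-baseline difference, so two programmers could classify the same patient differently.

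The default sentence adds a second problem. Failing to show progression and being impossible to assess lead to the same label.

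At stake are the baseline comparison listed in Table 3 and the subgroup tables of Section 4.5.5. The table of period durations by label is partly circular if duration helps determine the label.

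**Working it through.** **Inputs from the SAP.** FVC bar 50 mL per 6 months; steps bar 15%; 183 days per half-year; two 7-day windows; expected IPF decline 50 mL with SD 70 mL and 72 patients (Section 2.3). The SAP gives no numerical result for the labelling rule. Its nearest figure, the sample-size precision, reproduces: 1.96 × 70/√72 = 16.17 mL, for example 50 ± 16.17 = 33.83 to 66.17.

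**Step 1: the rate implied by a fixed bar.** Equivalent semi-annual change = bar × 183/T, with T in days after baseline.

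| T (days) | 15% steps | 50 mL FVC, only if raw |
|---|---|---|
| 30 | 91.5% | 305 mL |
| 90 | 30.5% | 102 mL |
| 365 | 7.5% | 25 mL |
| 530 | 5.2% | 17 mL |

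The steps column follows from the text. The FVC column applies only if the unscaled 7-day difference is used.

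**Step 2: overlapping windows.** Baseline is days 8–14. The last 7 days of an N-day series are days N−6 to N. They overlap baseline when N−6 ≤ 14, that is, with fewer than 21 days of data. At N = 14 they coincide, so the steps change is zero by construction, as is the FVC change under the 7-day reading.

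**Step 3: chance of the progressing label by follow-up.** The SAP gives no day-to-day variability, so these inputs are assumed: daily FVC SD s = 100 mL; steps falling by a mean of 5% (SD 20%) per 6 months; daily steps CV 20–40%; the two criteria independent; normal distributions. The 70 mL is taken as the between-patient SD. With T in months:

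- Raw FVC: mean 50T/6, variance (70T/6)² + 2s²/7.
- Slope FVC: mean 50, variance 70² + (183s)²/Sxx, where Sxx is the sum of squared deviations of the measurement days from their mean.
- Raw steps: mean 5T/6, variance (20T/6)² + 2(100·CV)²/7.
- Either criterion: 1 − (1 − pFVC)(1 − psteps).

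At 18 months, psteps = 0.50. Raw FVC gives 0.678 and slope FVC 0.50, so the label probabilities are 1 − 0.322 × 0.50 = 0.84 and 1 − 0.50 × 0.50 = 0.75. At 1 month, psteps = 0.103–0.256. Raw FVC gives 0.223 and slope FVC 0.50, so the results are 0.30–0.42 and 0.55–0.63.

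| Reading | 1 month | 6 months | 18 months |
|---|---|---|---|
| Both unscaled | 30–42% | 67–68% | 84% |
| FVC slope, steps raw | 55–63% | 67–68% | 75% |
| Both scaled to 6 months | 72–74% | 67–68% | 66% |

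Scaling both removes the rise with follow-up. A small excess from noise remains at short follow-up.

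**Step 4: noise in short series.** For n consecutive daily values, Sxx = n(n² − 1)/12, and the noise SD of slope × 183 is 183s/√Sxx. With s = 100 mL this is 18,300/√2,247.5 = 386 mL for 30 daily points and 18,300/√62,790 = 73 mL for 91, against a between-patient SD of 70 mL. A slope-based label therefore still needs a minimum series length.

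**The case against.** The strongest reply concerns FVC. The criterion is worded as a semi-annual decline, Section 4.5.1 time-adjusts that quantity, and the last sentence of the rule names it again. The 7-day sentence directly follows the steps clause and may explain only that clause. This stands: a reader might infer that the whole rule ignores follow-up, but for FVC the text is ambiguous rather than unscaled.

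A reader might also infer that the label largely reflects time in study, with short follow-up always pushing towards non-progressing. The documents do not support that. Under slope-based FVC the dependence is moderate. If the 7-day difference were instead rescaled to 183 days, the direction would reverse. For a truly stable patient, with assumed daily FVC SD 80–200 mL, the chance of exceeding the bar is 42–47% at 30 days and under 10% at 530 days.

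Nor does death force the label, since a patient who met either criterion beforehand is progressing. The SAP does not say how many patients will have very short series.

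It can be added that Section 4 allows a missing category in summaries and Section 4.8 generally rules out imputation, so unmeasured patients need not be called non-progressing. That helps little, because the default sentence is explicit and makes no exception for them.

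Finally, the study is descriptive and hypothesis-generating, Section 4.4.3.3 ties these subgroups to exploratory objectives, and the duration table would expose an imbalance. This limits the consequence. It does not give the label a consistent meaning, and Table 3 places the comparison under the secondary objectives.

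**Conclusion.** The point holds in three parts. The steps criterion is an unscaled change over variable follow-up. The FVC derivation is not fixed between slope × 183 and the 7-day difference. Patients who cannot be assessed are defaulted to non-progressing.

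The rates in Step 1 are plain arithmetic. The label probabilities rest on assumed variability and independence: from 1 to 18 months the rise is about 12 to 20 percentage points with slope-based FVC and about 42 to 54 if FVC is also unscaled. The label, and the baseline and duration tables split by it, therefore depend partly on time in study. The primary IPF estimate does not use the label and is unaffected. This should be corrected, but it does not threaten the main result.

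**What to change.** In Section 4.4.3.3:

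1. State that FVC progression means the Section 4.5.1 individual decline (slope × 183) exceeds 50 mL.
2. Define steps progression as a fall over 183 days, from the same regression on daily steps, of more than 15% of baseline. Remove the unclear absolute-difference wording.
3. Delete the last-7-days sentence, or limit it to whatever use remains.
4. Replace the default sentence so that non-progressing requires evaluable data, for example at least 30 days of measurements after baseline, the cut-off already used in Section 4.5.4. Put the remaining patients in a not-classifiable category that shows deaths and early treatment starts separately.
5. Repeat the tables, as a sensitivity analysis, in the subgroup Section 4.4.3.3 already defines with at least 3 months of observation. Step 4 shows why: 30-day slopes remain noisy. Three months is better as a sensitivity analysis than as the main rule, because it could remove fast decliners.

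The cost is SAP wording and one derivation. Somewhat fewer patients enter the progressing/non-progressing tables. Those left out may include fast decliners, so they should be described separately.

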4.4.3.4 IPF/ILD diagnosis

A listing and a frequency table will be provided for IPF and non-IPF ILD patients displaying details of the diagnosis (e.g. types of ILD, assessments used for diagnosis). In addition, information from working diagnosis for non-diagnosed patients will be tabulated and listed. Additionally, a Kaplan-Meier analysis is performed with respect to the time from enrollment to diagnosis, the time from enrollment to start of treatment, and time from diagnosis to start of treatment (for IPF and non-IPF ILD patients), presenting summary tables and corresponding KM plots separately by cohort. Thereby, the following rules for censoring will be applied:

- Time from enrollment to diagnosis (in weeks):

F. Hoffmann-La Roche Ltd
Statistical Analysis Plan MA39297, Final Version 2.0

Only diagnosed patients will be analyzed separately by cohort. For that reason, there will be no censoring observations.

- Time from enrollment to start of treatment (in weeks):

If a patient was diagnosed and did not start IPF/ILD treatment during the post-diagnosis period or is lost to follow-up, the patient will be censored at the time of the end of study visit, or at the last available visit during the post-diagnosis period. Frequencies of patients with events and without events, i.e. that treatment was initiated or not, will be presented together with the KM estimates.

- Time from diagnosis to start of treatment (in weeks):

If a patient was diagnosed and did not start IPF/ILD treatment during the post-diagnosis period or is lost to follow-up, the patient will be censored at the time of the end of study visit, or at the last available visit during the post-diagnosis period. Frequencies of patients with events and without events, i.e. that treatment was initiated or not, will be presented together with the KM estimates.

The duration of pre- and post-diagnosis periods is analyzed by use of a summary table.

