The diagnosis of IPF carries a bleak prognosis, with progressive disability due to respiratory insufficiency (Hallstrand et al. 2005). Data from the placebo arm of several controlled clinical trials suggest that the rate of decline in forced vital capacity (FVC) in patients with IPF is approximately 150 to 200 mL/yr in patients with IPF (Demedts et al. 2005; Ley et al. 2011; Raghu et al. 2004, 2008). Estimated survival, in the absence of treatment, is between three to five years after diagnosis (American Thoracic Society and European Respiratory Society 2002; Bjoraker et al. 1998; Douglas et al. 2000; Gribbin et al. 2006; Hyldgaard et al. 2014; Kim et al. 2006; Mapel et al. 1998; Olson et al. 2007).

A diminished quality of life in patients with IPF is well established, with impaired energy level and decreased level of independence in concert with respiratory symptoms (Swigris et al. 2005).

To date, two anti-fibrotic drugs have been approved for use in IPF: pirfenidone and nintedanib; both therapies have shown to significantly slow the progression of lung function decline in IPF (Raghu et al. 2015), although the disease remains incurable.

In terms of current clinical practice, there are limited data available on the early course of disease in symptomatic patients with suspicion of IPF/ILD. Thus, the peri-diagnosis period (see definition in Section 2.2) including the pre- and post-diagnosis periods is critical to the assessment of disease behavior, the timely accurate diagnosis and the decision to treat. The study will not focus on asymptomatic stages of disease when discovery would rely on imaging techniques for lung cancer screening purposes or incidental finding.

This study will characterize the disease behavior of IPF and ILD patient in the peri-diagnostic period, having as aim to increase the knowledge of the progressive nature of IPF/ILD already at early phases of assessment.

This objective will be achieved using a multidimensional approach assessing changes in pulmonary function, measured by daily handheld spirometry as well as assessing physical functional capacity.

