4.2.4 Post-diagnosis Assessment Period

Patients diagnosed with IPF or non-IPF ILD at Visit 2 will remain and be followed in the study up to the start of drug treatment (within 6 months) or a maximum of 6 months if no drug treatment is prescribed.

“Start of drug treatment” is defined as the date the treatment is planned to commence. This includes the event of a patient receiving IPF or ILD drug treatment from a physician other than the investigator.

The length of the post-diagnosis period is thus defined as:

Post-diagnosis period = date of start of drug treatment – date of initial diagnosis or
= date of end of study visit – date of initial diagnosis

whichever comes first, where diagnosis date is taken from the IPF/ILD diagnosis eCRF page. In addition, any data point collected after initiation of treatment until EOS visit will be excluded from any analysis.

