4.7 SAFETY ANALYSES

4.7.1 Safety Endpoints

The following safety endpoints will be analyzed descriptively by diagnosis cohorts:

- **Non-elective hospitalization, both respiratory and all cause:** a listing and a frequency table will be provided displaying number of patients with at least one non-elective hospitalization, the number of non-elective hospitalizations, the number of patients with at least one respiratory-related non-elective

hospitalization and the number of respiratory-related non-elective hospitalizations during pre- or post-diagnosis periods by diagnosis cohorts.

- **Investigator-reported acute exacerbations:** a listing and a frequency table will be provided displaying number of patients with at least one acute exacerbation and number of acute exacerbations during pre- and post-diagnosis periods by diagnosis cohorts. Additionally, number of patients and events will be given separately for triggered and idiopathic acute exacerbations. Acute exacerbation are defined as per Collard et al. 2016: answering No to the eCRF question “Is there an extra-parenchymal cause identified?”; and answering Yes to the eCRF question “Are there new, bilateral GGO (Ground glass opacification)/ consolidation on CT?” Please refer to [Appendix 8](#) for further information.
- **Death, all cause and respiratory-related:** a listing and a frequency table is given including number of deaths during pre- and post-diagnosis period, primary cause of death and frequencies with respect to autopsies performed.
- **Events related to the study assessments:** documented events will be coded with MedDRA version 21.1 or a higher one. Frequencies of events will be displayed by System Organ Class (SOC) and Preferred Terms (PT) by diagnosis cohorts. In addition, summary of the events characteristics, events by intensity and leading to study discontinuation will be presented separately. The tables will be provided for events occurring during the peri-diagnosis period. If the start date of an event is after or on the day of the enrollment visit or it is ongoing at enrollment visit and the end date of the event is after the day of the initial diagnosis visit, the event belongs to the peri-diagnosis period. A listing with all events will be also presented.

If for any of the above mentioned events an incidence rate of more than 15% is observed, time to event analyses according to the method of Kaplan-Meier will additionally be provided.

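### The Kaplan-Meier rule for time to treatment start does not name death, so untreated deaths are censored by default and uptake is slightly overstated

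*SAP*

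**What the plan says.** In SAP section 4.4.3.4, "a Kaplan-Meier analysis is performed with respect to the time from enrollment to diagnosis, the time from enrollment to start of treatment". Time from diagnosis to start of treatment is handled in the same way, for IPF and non-IPF ILD patients, with tables and plots by cohort.

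Both treatment-start analyses share one censoring rule for diagnosed patients: "did not start IPF/ILD treatment during the post-diagnosis period or is lost to follow-up, the patient will be censored at the time". The time meant is that "of the end of study visit, or at the last available visit during the post-diagnosis period". The section adds: "Frequencies of patients with events and without events, i.e. that treatment was initiated or not, will be presented together with the KM estimates".

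Section 4.2.4 follows diagnosed patients "up to the start of drug treatment (within 6 months) or a maximum of 6 months if no drug treatment is prescribed".

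Death appears elsewhere. Section 2.2.4 has deaths recorded in the eCRF, and under section 4.7.1 "a listing and a frequency table is given including number of deaths during pre- and post-diagnosis period". On prognosis, the Background (section 1) says of IPF: "Estimated survival, in the absence of treatment, is between three to five years after diagnosis". No 6-month death rate is given, and no survival figure is given for non-IPF ILD.

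**The concern.** Censoring is harmless when the censored patient could still have the event at the same rate as those who stay under observation. A patient who is alive and untreated at 6 months, when follow-up ends by design, meets that condition. A patient who has died does not, because death rules out treatment start.

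The rule in section 4.4.3.4 does not distinguish the two. A patient who dies untreated satisfies its condition of not having started, and no other rule in the SAP applies. Such a patient therefore leaves the risk set as ordinary censoring. One minus Kaplan-Meier then estimates uptake in a hypothetical setting without death, not the proportion of patients who start. The error can only be upward.

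Censoring at a visit adds to it. A patient who dies has no end of study visit, so the rule points back to the last available post-diagnosis visit, before the death.

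What is at stake is the reading of the curves: a reader who takes 1 minus Kaplan-Meier at 6 months as the share treated gets a figure that is somewhat too high.

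**Working it through.** The plan states no figure for this output, so there is none to reproduce. The check asks how large the overstatement could be.

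**Inputs**
- Horizon T = 0.5 years after diagnosis (section 4.2.4).
- Survival of 3 to 5 years without treatment (section 1, IPF only). Assumption: this is a median, and the hazard is constant.
- About 72 IPF patients (section 2.3).
- Proportion starting treatment by 6 months: not in the plan. Assumption: F, the 1 minus Kaplan-Meier value, lies between 30% and 90%, with a constant hazard independent of death.

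**Death hazard**
- Median 5 years: d = ln 2 / 5 = 0.139 per year. Six-month mortality if nobody is treated: 1 − exp(−0.139 × 0.5) = 6.7%.
- Median 3 years: d = ln 2 / 3 = 0.231 per year. Six-month mortality: 1 − exp(−0.231 × 0.5) = 10.9%.

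**Two estimands**
- With deaths censored at the time of death, 1 minus Kaplan-Meier targets F = 1 − exp(−hT), so h = −ln(1 − F)/T.
- The true share starting treatment is the cumulative incidence, CIF = h/(h + d) × [1 − exp(−(h + d)T)].

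Worked case, F = 50%: h = ln 2 / 0.5 = 1.386 per year.
- Median 5 years: 1.386/1.525 × [1 − exp(−0.762)] = 0.909 × 0.533 = 48.5%, a gap of 1.5 points.
- Median 3 years: 1.386/1.617 × [1 − exp(−0.809)] = 0.857 × 0.555 = 47.5%, a gap of 2.5 points.

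| 1 − KM | CIF, median 5 y | Gap (points) | CIF, median 3 y | Gap (points) |
|---|---|---|---|---|
| 30% | 29.0% | 1.0 | 28.4% | 1.6 |
| 50% | 48.5% | 1.5 | 47.5% | 2.5 |
| 70% | 68.1% | 1.9 | 66.9% | 3.1 |
| 90% | 88.0% | 2.0 | 86.7% | 3.3 |

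**Deaths before treatment.** The share is d/(h + d) × [1 − exp(−(h + d)T)]. It runs from 2.7% to 5.6% (about 2 to 4 of 72) at a median of 5 years, and from 4.4% to 9.2% (about 3 to 7 of 72) at 3 years. These are below the 6.7% and 10.9% above because follow-up stops at treatment start.

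**Sensitivity**
- Reading 3 years as a mean (d = 1/3 per year) gives gaps of 2.2 to 4.6 points.
- A simulation of 400,000 patients per scenario agrees with the table. Moving deaths back to an assumed last visit, at diagnosis or month 3, gives gaps of about 1.4 to 4.0 points.

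**Scale.** The 95% half-width for a 50% proportion in 72 patients is 1.96 × √(0.5 × 0.5 / 72) = 0.115, or about 11.5 points.

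**The case against.** The best defence is that the share treated is already reported. The counts with and without treatment start stand beside the Kaplan-Meier estimates, and section 4.4.1 tabulates patients with and without start of treatment, with reasons for early discontinuation. Follow-up after diagnosis is capped at 6 months, so without other early loss the crude proportion is the end-of-period cumulative incidence. The SAP never calls 1 minus Kaplan-Meier uptake. Time to treatment start is not an endpoint in Table 3 of Appendix 1, section 2.3 describes the purpose as hypothesis generation and estimation, and the bias is well inside sampling error.

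Most of this stands and makes the point minor. Two parts do not fully answer it. The censoring rule itself expects loss to follow-up. With such losses the crude share is too low while 1 minus Kaplan-Meier is too high, and cumulative incidence deals with both. An end-of-period count also cannot correct a curve plotted over time.

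A reader might infer more than the SAP supports:
- That it prescribes censoring at death. It is silent on death, and censoring is only the default outcome of the rule.
- That death within 6 months is known to be common here. That rests on converting a survival range for untreated IPF, and nothing comparable is given for non-IPF ILD.
- That comparisons between cohorts or site types are distorted. No death rates by cohort or site type are given, and the gap also depends on the treatment-start rate.
- That the same fault holds in section 4.7.1, where "time to event analyses according to the method of Kaplan-Meier will additionally be provided" for safety events. Those curves depend on an incidence above 15%, no censoring rule is stated for them, and no size can be attached.

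**Conclusion.** The point holds as a minor one. Section 4.4.3.4 leaves death before treatment to ordinary censoring by omission, and no competing-risk method is planned anywhere in the SAP. The direction of the error is certain. Its size at 6 months is about 1 to 3 percentage points in IPF, and under 5 points in the least favourable variant examined.

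The size rests on three assumptions: the survival range is a median, both hazards are constant and independent, and 30% to 90% start treatment within 6 months. It does not carry over to the non-IPF ILD cohort. The primary endpoint is unaffected.

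**What to change.** - **From diagnosis:** state that death before treatment start is a competing event. Report the Aalen-Johansen cumulative incidence of treatment start, with the curve for death before treatment beside it. Time the death at its actual date, not at the last visit.
- **From enrollment:** use the same method and label the result as conditional on having been diagnosed. The analysis takes diagnosed patients by cohort, so deaths before diagnosis are excluded by construction and the result is not the share of all enrolled patients who start treatment.
- **Keep** the crude counts next to the estimates.

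The cost is a few lines of SAP text, slightly more programming and one more curve. Deaths are already collected, and section 4.7.1 already assigns them to the pre- or post-diagnosis period, which needs their timing.
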